3.5.2.1 Screening Assessments

All subjects will have undergone a CT identifying at least one abdominal solid organ injury prior to being approached for the study. If the CT was performed at a referring institution, the CT will

be delivered to the participating institution and will be re-read at the participating institution by study staff. Study personnel will assess all inclusion and exclusion criteria for each potential subject. Only subjects who meet all criteria will be consented into the study.

Subjects may be consented and enrolled at any time during their hospital stay as long as the study procedures can be performed within 48 hours of injury.

The de-identified CTs for all enrolled subjects will be sent to a repository at Boston Children's Hospital, the coordinating center, for a central read.

3.5.2.2 Assessments during Study Procedure

Subjects will be transported to the Radiology department for the study treatment. If the subject is in the ICU, bedside ultrasounds may be performed instead of moving to the Radiology department. The sonographer will first perform a greyscale/doppler ultrasound and record findings, including presence or absence of injury for each organ, grade of injury if applicable, presence or absence of peritoneal fluid, and approximate amount of fluid if applicable. Licensed study personnel will then inject the contrast agent and the sonographer will perform a CEUS and record the same findings as listed above. A second injection will be given a minimum of ten minutes after the first injection to complete the CEUS procedure. Any physical findings on the abdomen will also be recorded.

The ultrasounds for all enrolled subjects will be sent to a repository at Boston Children's Hospital, the coordinating center, for a central read.

3.5.2.3 Follow-up Assessments

All patients will be maintained on a cardiopulmonary monitor as a standard part of the clinical care of their injury. Vital signs, including blood pressure, heart rate, respiratory rate, and oxygen saturation will be monitored prior to the injection of the contrast agent and continuing for 30 minutes after the final injection. The vital signs will be recorded at 5 minute intervals by the study personnel. The study personnel will ask the patient about any side effects he/she experiences pre-contrast injection, after each contrast bolus, and at the completion of the 30 minute observation period.

After the completion of the ultrasounds, subsequent patient care will be as otherwise indicated per the trauma team for the management of their injuries.

3.5.3 Assessment of Safety

Patients will be monitored for adverse events for 30 minutes after completion of the final contrast injection.

3.5.3.1 Adverse Events

3.5.3.1.1 Definition of Adverse Events

For purposes of this study, an adverse event will be defined as any unfavorable and unintended diagnosis, symptom, sign, syndrome or disease which either occurs during the study, having been absent at baseline, or, if present at baseline, appears to worsen.

An unexpected adverse event will be defined as any adverse event that is not listed as a risk in the current version of the Protocol or Package Insert.

An adverse reaction will be defined as any adverse event caused by the Investigational Product. A suspected adverse reaction will be defined as any adverse event for which there is a reasonable possibility that the Investigational Product caused the event.

All adverse events will be graded by the site investigator according to the criteria specified by the Common Terminology Criteria for Adverse Events (CTCAE) Version 4.03 (NIH, June 14, 2010).

Adverse events that have been reported as possibly related to the study procedure include the following: headache, nausea, dysgeusia, injection site warmth or pain, feeling hot, chest discomfort or pain, dizziness, cardiopulmonary reactions, and hypersensitivity reactions.

3.5.3.1.2 Definition of Serious Adverse Events

An AE occurring with any study treatment regimen should be classified as “Serious” if it meets one of the following criteria:

- It results in death (ie, the AE caused or led to death).

- It is life threatening (ie, the AE placed the subject at immediate risk of death). This classification does not apply to an AE that hypothetically might cause death if it is more severe.
- Event severe enough to require airway management, ICU admission, hypotension requiring fluid or IV vasopressor administration.
- It requires or prolongs inpatient hospitalization (ie, the AE requires at least a 24-hour inpatient hospitalization or prolongs a hospitalization beyond the expected length of stay). Hospitalizations for elective medical or surgical procedures, scheduled treatments, or routine checkups are not SAEs by this criterion.
- It is disabling or incapacitating (ie, the AE results in a substantial disruption of the subject's ability to carry out normal life functions).
- It is a congenital anomaly or birth defect (ie, an adverse outcome in a child or fetus of a subject exposed the molecule or study treatment regimen before conception or during pregnancy).
- It does meet any of the above criteria, but could jeopardize the subject and might require medical or surgical intervention to prevent one of the outcomes listed above.
- Any other CTCAE event of grade 3 or greater deemed possibly or definitely related to the study drug.

3.5.3.1.3 *Documentation and Reporting of Adverse Events*

The severity of toxicities will be graded in accordance with the Common Terminology Criteria for AE (CTCAE) version 4.0.3. Grade 2 AEs deemed possibly, probably, or definitely related to study medication and all Grade 3 and higher AEs, regardless of suspected causal relationship to study drug, will be recorded as AEs in the CRFs.

All SAEs must be reported to the Sponsor or designee within 24 hours of site awareness, regardless of the relationship of the event to the study treatment regimen. Refer to the previous section for the definition of a serious adverse event. The completed SAE form will be scanned and emailed securely within 24 hours to the Sponsor at [contact]

and [name] at [contact]. Relevant follow-up information will be submitted to the Sponsor or its designee as soon as it becomes available.

Boston Children's Hospital PI will inform the DSMB, as well as the Boston Children's Hospital IRB according to Institutional guidelines for reporting. The occurrence of 2 or more serious adverse events will result in a pause in the study while an investigation is conducted by the DSMB to determine if the study should resume.

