3.6 SAFETY ISSUES RELATED TO INVESTIGATIONAL PRODUCT

Anticipated Risks

All patients will have at least one functioning intravenous catheter in place as a part of standard medical care and no new IV access will be required. We expect that there may be some mild discomfort related to the performance of the ultrasound study itself and will monitor for this. Other than the discomfort from the ultrasound probe, we do not expect any other ultrasound-related adverse events. Patients will be monitored during the study interval and for 30 minutes after final contrast injection by licensed study personnel, and only hemodynamically stable patients will be selected, making it very unlikely that there will be a hemodynamic issue during the brief time of the study.

Licensed study personnel will administer Lumason and monitor the patient during injection and for 30 minutes afterward for any adverse effects. A questionnaire will be filled out during the study to record any potential reactions to Lumason. Resuscitation equipment and trained personnel will be available during the administration of Lumason and the follow-up period.

Reported risks related to Lumason administration include:

Adverse Reactions in 6,856 patients receiving Lumason		
Adverse Reaction	Number	(%)
Any Adverse Reaction	340	5
Headache	65	1
Nausea	37	0.5
Dysgeusia	29	0.4

October 16, 2019

Injection site pain	23	0.3
Feeling hot	18	0.3
Chest discomfort	17	0.2
Chest pain	12	0.2
Dizziness	11	0.2
Injection site warmth	11	0.2

Serious cardiopulmonary reactions, including fatalities, have occurred uncommonly in adults during or shortly following administration of ultrasound contrast agents, including Lumason. These reactions typically occurred within 30 minutes of administration. Hypersensitivity reactions such as skin erythema, rash, urticaria, flushing, throat tightness, dyspnea, or anaphylactic shock have uncommonly been observed following the injection of Lumason. The exclusion criteria eliminate any subjects with a known cardiac abnormality or a known sensitivity to sulfur hexafluoride, so we do not anticipate that these reactions will occur. As stated above, resuscitation personnel and equipment will be available during the study treatment and follow-up period.

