3.8.5 Safety Analysis

All subjects who receive study drug will be analyzed for safety. The proportion of patients with specific adverse events will be reported as well as the worst grade observed across all adverse events. The maximum confidence interval width for these estimates is 17.6%. If the observed estimated adverse event proportion is 10%, the 95% confidence interval is (5.5,16.4%).

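### The adverse event recording rule in 3.5.3.1.3 cannot supply the all-adverse-event tables that 3.8.5 promises (minor)

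*Combined protocol and SAP*

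**What the plan says.** Three parts of the combined protocol and SAP bear on which adverse events are counted.

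- **Definition and grading (3.5.3.1.1).** For this study "an adverse event will be defined as any unfavorable and unintended diagnosis, symptom, sign, syndrome or disease" that arises or worsens during the study. There is no floor on severity and no condition on cause. The same section, and the synopsis, have every AE graded under CTCAE 4.03.
- **Recording (3.5.3.1.3).** What is entered as an AE on the CRFs is "Grade 2 AEs deemed possibly, probably, or definitely related to study medication and all Grade 3 and higher AEs", the second group whatever the suspected cause.
- **Analysis (3.8.5).** "The proportion of patients with specific adverse events will be reported as well as the worst grade observed across all adverse events". The population is everyone who receives study drug.

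Two other routes could pick up milder events. In 3.5.2.3, "The study personnel will ask the patient about any side effects he/she experiences pre-contrast injection", and again after each bolus and at the end of the 30-minute observation. In 3.6, "A questionnaire will be filled out during the study to record any potential reactions to Lumason". Section 3.7.1 places all research data on CRFs.

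Section 3.6 also names an event that it expects: "We expect that there may be some mild discomfort related to the performance of the ultrasound study itself and will monitor for this". It then treats this as an AE: "Other than the discomfort from the ultrasound probe, we do not expect any other ultrasound-related adverse events".

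**The concern.** The analysis is stated for all AEs, but the only rule on what becomes an AE record admits a subset. An analyst who builds the 3.8.5 tables from the AE records will report a different quantity from the one 3.8.5 names, and the table label will not show it. Another analyst, reading 3.8.5 literally, might add the questionnaire and side-effect answers and produce different tables from the same trial.

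What is at stake is the descriptive safety summary of a contrast agent in children. Its main content is likely to be mild, transient symptoms, because the reactions listed in 3.6 are mostly of that kind (headache, nausea, altered taste, injection-site symptoms).

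**Working it through.** **1. The plan's own figures.** Section 3.8.5 gives a 95% interval of 5.5% to 16.4% for an observed 10%, and a maximum width of 17.6%. Exact Clopper-Pearson limits with n = 132:

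- x = 13.2 (exactly 10%): 5.46% to 16.43%.
- x = 66 (50%): 41.18% to 58.82%, width 17.64%.

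Both reproduce. The arithmetic is sound; the open matter is which events the proportions count.

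**2. The sections side by side.**

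| Event | AE under 3.5.3.1.1 | Entered as AE under 3.5.3.1.3 | Within 3.8.5 as worded |
|---|---|---|---|
| Grade 1, any cause | yes | no | yes |
| Grade 2, not related to the drug | yes | no | yes |
| Grade 2, related to the drug | yes | yes | yes |
| Grade 3 or higher, any cause | yes | yes | yes |

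The first two rows are the mismatch. Removing events can only lower a proportion or leave it unchanged, so estimates from the AE records are at or below the all-AE proportions. A worst-grade table from the same records starts at Grade 2.

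**3. The expected event.** Under 3.5.2.2, "The sonographer will first perform a greyscale/doppler ultrasound and record findings", before any contrast is given. Discomfort from the probe at that stage cannot be due to the study drug, and later probe discomfort is still caused by the probe. It therefore fails the relatedness test at Grade 2 and is not entered at Grade 1. Below Grade 3, an event that 3.6 both predicts and promises to monitor leaves no AE record.

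**4. The other capture routes.** The side-effect questions are broad enough to elicit mild symptoms. The questionnaire is aimed at reactions to the drug, so it does not clearly cover the probe. Any answer that meets the AE definition must be graded under 3.5.3.1.1. The text does not say that these answers become AE records, that they carry a relationship assessment, or that they feed 3.8.5.

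**5. Scale.** Inputs: 132 patients (3.8.1) and the reaction counts among 6,856 patients (3.6). I assume that the counts are of patients, that the rates carry over to this trial, and that 132 patients are dosed.

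- One patient: 1/132 = 0.76 percentage points.
- Any reaction: 340/6,856 = 4.96%, and 132 × 340/6,856 = 6.5 patients.
- Headache: 132 × 65/6,856 = 1.25 patients.
- Nausea: 132 × 37/6,856 = 0.71. Dysgeusia: 132 × 29/6,856 = 0.56.
- The other six listed reactions: from 132 × 11/6,856 = 0.21 to 132 × 23/6,856 = 0.44.

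Let s be the share of reacting patients whose reactions are all Grade 1. The AE records would then show 4.96% × (1 − s): 4.96%, 3.72%, 2.48%, 1.24% and 0% at s = 0, 25, 50, 75 and 100%. The documents give no value for s, so this range illustrates the mechanism and does not estimate the loss. It also covers drug reactions only and says nothing about the frequency of probe discomfort.

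**The case against.** The best defence is that 3.8.5 does state its scope. It says all AEs, and that term is defined in 3.5.3.1.1 without a grade limit. Every AE must be graded, research data go on CRFs, and patients are asked about side effects at several times. On that reading an all-grade table is intended and could be produced. A recording threshold is also a legitimate choice, and a broad definition beside a narrower recording rule is not in itself a contradiction.

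Much of this stands, and it rules out three stronger readings that a reader might infer:

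- *Mild events are not collected at all.* Not supported: 3.5.2.3 and 3.6 provide routes that may capture them.
- *The plan does not provide for grading mild events.* Not supported: 3.5.3.1.1 and the synopsis require all AEs to be graded.
- *Section 3.8.5 has no scope.* Not supported: it says all AEs. The fault is a mismatch with 3.5.3.1.3, not a missing scope.

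The defence does not remove the mismatch. Grading every event, entering some of them as AEs and reporting on all of them do not fit together unless the text says how the events not entered reach the analysis.

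Two limits are fair. The contents page lists an Appendix I that is not in the text reviewed, and the CRFs and questionnaire are not included either, so the statement that nothing links them to 3.8.5 applies only to the supplied text. Also, eight of the nine listed reactions have expected counts below one, so several rows may be empty under any rule.

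**Conclusion.** The point holds as a minor inconsistency. As written, the recording rule cannot deliver the analysis stated in 3.8.5. If the AE records are the source, the specific-event proportions equal or understate the all-AE proportions, Grade 1 cannot appear in the worst-grade table, and mild probe discomfort is lost.

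The direction is conditional on that source, and the size is unknown. The expected 6.5 patients with any reaction, and 0.76 points per patient, give scale only and rest on the assumptions listed with them. A reader might infer that the reported rate will be low by some definite amount, or that serious harm could be hidden. The documents support neither: there is no grade split, and serious events are reported separately on an SAE form whatever their relationship to treatment. Efficacy, SAE reporting and the pause after two SAEs do not depend on this rule.

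**What to change.** Reconcile 3.5.3.1.3 with 3.8.5 in one of two ways.

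1. **Record everything.** In 3.5.3.1.3, enter AEs of every grade and relationship over the study procedure, from the start of the greyscale/Doppler scan to the end of the 30-minute observation. Use the grading already required and the side-effect questions already asked, and add a question on probe discomfort. Hold grade and relationship as data fields, not entry filters. In 3.8.5, name these records as the source and report by grade, all-cause and related-only.
2. **Keep the threshold and relabel.** In 3.8.5, describe the estimates as related Grade 2 and any Grade 3 or higher events, and drop the reference to all AEs.

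The first option costs more CRF entries and gives a higher all-cause rate. That rate will include some symptoms of the injury itself, because every patient has an acute abdominal injury and worsening of a baseline symptom counts as an AE; the related-only rate is reported beside it for that reason. The second costs one sentence, but the tables will then not describe mild events. Either option removes the inconsistency, and neither changes SAE reporting.

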3.6 SAFETY ISSUES RELATED TO INVESTIGATIONAL PRODUCT

Anticipated Risks

All patients will have at least one functioning intravenous catheter in place as a part of standard medical care and no new IV access will be required. We expect that there may be some mild discomfort related to the performance of the ultrasound study itself and will monitor for this. Other than the discomfort from the ultrasound probe, we do not expect any other ultrasound-related adverse events. Patients will be monitored during the study interval and for 30 minutes after final contrast injection by licensed study personnel, and only hemodynamically stable patients will be selected, making it very unlikely that there will be a hemodynamic issue during the brief time of the study.

Licensed study personnel will administer Lumason and monitor the patient during injection and for 30 minutes afterward for any adverse effects. A questionnaire will be filled out during the study to record any potential reactions to Lumason. Resuscitation equipment and trained personnel will be available during the administration of Lumason and the follow-up period.

Reported risks related to Lumason administration include:

Adverse Reactions in 6,856 patients receiving Lumason		
Adverse Reaction	Number	(%)
Any Adverse Reaction	340	5
Headache	65	1
Nausea	37	0.5
Dysgeusia	29	0.4

October 16, 2019

Injection site pain	23	0.3
Feeling hot	18	0.3
Chest discomfort	17	0.2
Chest pain	12	0.2
Dizziness	11	0.2
Injection site warmth	11	0.2

Serious cardiopulmonary reactions, including fatalities, have occurred uncommonly in adults during or shortly following administration of ultrasound contrast agents, including Lumason. These reactions typically occurred within 30 minutes of administration. Hypersensitivity reactions such as skin erythema, rash, urticaria, flushing, throat tightness, dyspnea, or anaphylactic shock have uncommonly been observed following the injection of Lumason. The exclusion criteria eliminate any subjects with a known cardiac abnormality or a known sensitivity to sulfur hexafluoride, so we do not anticipate that these reactions will occur. As stated above, resuscitation personnel and equipment will be available during the study treatment and follow-up period.

3.7 DATA QUALITY ASSURANCE

Accurate, consistent, and reliable data will be ensured through the use of standard practices and procedures. These are described in the following sections.

3.7.1 Data Collection, Monitoring, and Transfer

All clinical research data will be recorded and maintained on study specific case report forms (CRFs). These CRFs will be stored within individual subject binders in accordance with Good Clinical Practice Standards. Study materials will be kept in designated locked file cabinets and access will be restricted to authorized study staff only. Subject confidentiality will be maintained by recording subject-specific data using a unique confidential study identifier.

All study data will be entered into a REDCap database and monitored for data accuracy. Data and source documents will be maintained in compliance with ICH-GCP and local and national regulatory requirements.

The coordinating center will maintain a central repository of all de-identified CT and US scans for all subjects across all sites in order to provide the scans to the central reviewers.

3.7.2 Data and Safety Monitoring Plan

A Data and Safety Monitoring Board (DSMB) will be created with members with expertise in ultrasonography, statistics, and trauma surgery. The DSMB will meet at a minimum of twice per year. Details of the reporting procedures to the DSMB are included in the DSMB Charter. The DSMB will provide recommendations to change the study or to continue the study.

3.7.3 Study Monitoring and Auditing

This study will be monitored in accordance with the BCH Program Data Safety Monitoring Plan. Monitoring and auditing procedures as outlined in the BCH Program Data Safety Monitoring Plan will be followed to ensure that the entire study is conducted, documented, and reported in accordance with the IRB approved protocol, the International Conference on Harmonization (ICH) Good Clinical Practice (GCP) guidelines, and applicable regulatory requirements of Boston Children's Hospital.

Monitoring of timeliness of Adverse Event and Serious Adverse Event reporting will be done as events are reported to the coordinating center. Case report forms for each subject enrolled into the study will be monitored for completeness and quality.

3.8 STATISTICAL METHODS PLANNED IN THE PROTOCOL AND DETERMINATION OF SAMPLE SIZE

3.8.1 Sample Size and Power Considerations

Sample size for the study was determined based on the precision of the confidence interval for the primary endpoint. This approach will be considered promising if the true proportion of subjects with all injuries identified by CT also identified by CEUS is greater than or equal to 90%. Assuming we observe 90% of subjects with all injuries identified by CT and by CEUS, a sample size of 132 patients will attain a two-sided 95% confidence interval with a width equal to 11%, with exact Clopper-Pearson lower and upper confidence limits of 83.6% and 94.5% respectively. For secondary endpoints, a sample size of 132 patients will produce 95% confidence intervals with a maximum width of 17.6%.

3.8.2 Statistical Analysis Plan

We will summarize patient demographic and clinical characteristics using descriptive statistics: means, standard deviations, medians, and ranges for continuous measures; frequencies and proportions for categorical measures. For the primary objective, we will calculate the proportion and 95% confidence interval. For the secondary objectives, we will calculate the proportion and 95% confidence interval. We will also report the sensitivity and specificity of the CEUS relative to CT in identifying individual organ abnormalities in separate models and combined models. In the combined analysis, sensitivity and specificity will be estimated using random effects model or generalized estimating equations to adjust for potential correlation between organs within an individual. Statistical analysis will be performed using standardized packages (SPSS version 19.0 from SPSS Inc./IBM, Chicago, IL or SAS version 9.4 from SAS Institute Inc., Cary, NC.)

